4.2.1. Participant Input into Design

Not applicable as this is a study in healthy participants.

4.3. Justification for Dose

The 15 mg dose to be used in the Two-way Crossover Period of the study has been chosen because it is the dose most commonly used in the ongoing Phase 3 Study WTX101-301 and is expected to be the prescribed starting dose in adult and adolescent patients with WD aged 12 years and older.

The 15 mg tablet is the only dose strength currently available as a reference dose for the relative bioavailability test. If a dose of 30 mg or greater is required, a patient with WD will be administered 2 or more 15 mg EC tablets, rather than ≥ 24 EC mini-tablets.

The EC mini-tablet doses of 2.5, 5, 10, and 30 mg to be tested in the Dose-Proportionality Extension Period of the study, in addition to the 15 mg dose to be tested in the Two-way Crossover Period, will cover the entire anticipated dose range recommended in the planned study in the pediatric population. Selection of the starting and maximum doses for the planned study in the pediatric population aged 3 to < 12 years is based on a combination of standard body weight based allometric principles and age-based changes in liver volume. To support the dose selection, PK simulations were conducted based on the allometric scaling of population PK model using PK data (ie, total Mo) from Study WTX101-201 in patients with WD and Study WTX101-102 in healthy participants who were administered the EC tablet. The general approach of dose selection for pediatric investigation used here is consistent with the United States Food and Drug Administration guidance (<https://www.fda.gov/media/90358/download>) as well as European Medicines Agency (EMA) guidance ICH E11(R1) (EMA, 2017).

For patients aged 3 to < 12 years, a lower starting dose of 2.5 mg/day will be administered for 4 weeks based on scaling of the starting dose of 15 mg/day in patients with WD aged 12 years and above in the ongoing Phase 3 Study WTX101-301. After 4 weeks, up titration to 5 mg once daily may be performed at the discretion of the Investigator, if the disease is not adequately controlled, taking into account the patient's clinical status and free blood Cu concentration based on pre-defined criteria, as measured by LBC, and provided none of the dose modification criteria apply. Further dose increases up to a maximum dose of 30 mg/day in 5 mg increments at least 4 weeks apart are possible at the discretion of the Investigator following the same aforementioned criteria.

For patients aged 3 to < 6 years, the population PK modeling results showed that a 5 mg dose has comparable exposure to 15 mg administered to adult patients, and that a 15 mg dose has a higher exposure than 30 mg, but a lower exposure than 60 mg administered to adult patients. Hence, the predicted dose range for patients aged 3 to < 6 years is 5 mg to 15 mg, which is anticipated to provide comparable safety and efficacy outcomes to those in adolescent and adult patients over 12 years of age with a dose range of 15 mg to 60 mg currently allowed in the ongoing Phase 3

Study WTX101-301. Therefore, the EC mini-tablet doses of 2.5, 5, 10, 15, and 30 mg will be tested in this study, which covers the entire anticipated dose range recommended in the planned study in the pediatric population.

An inductively coupled plasma-mass spectroscopy (ICP-MS) method, with a lower limit of quantification (LLOQ) of 1.00 ng/mL and 0.25 ng/mL for the assays of total Mo and PUF Mo, respectively, has been previously implemented for analyzing plasma samples from Study WTX101-HV-106. In that study, for the 15 mg and 60 mg doses, %AUC_{extrap} ranged from 1.3% - 12.2% (all were less than 20%). In the current study, a maximum observed concentration (C_{max}) for total Mo of approximately 40 ng/mL is anticipated after the lowest ALXN1840 dose of 2.5 mg and with an assay LLOQ of 1.00 ng/mL, it would be possible to detect measurable total Mo concentrations at a mean of 1.25 ng/mL for approximately 5 half-lives with reasonably low expectation for excess AUC extrapolation of over 20% for AUC_∞ estimation. A C_{max} for PUF Mo of approximately 2 ng/mL is anticipated after the lowest ALXN1840 dose of 2.5 mg and with an assay LLOQ of 0.25 ng/mL, it would be possible to detect measurable PUF Mo concentrations at a mean of 0.25 ng/mL for approximately 3 half-lives with possibility of AUC extrapolation of over 20% for AUC_∞ estimation.

4.4. End of Study Definition

The planned study duration is approximately 10 weeks, which includes an up to 28-day Screening period, 2 periods of approximately 11 days in the Two-way Crossover Period (with at least 14 days from the previous dose of ALXN1840 before the next dose is administered), plus a 14 -day period in the Dose--Proportionality Extension Period (again, 11 days in the CRU with at least 14 days from the previous dose before the next dose is administered).

The EOS for each participant is defined as completion of the EOS Visit on Day 15 ± 2 days of the Dose-Proportionality Extension Period.

The EOS is defined as the date of the last participant's last scheduled visit (ie, the last visit as scheduled/foreseen by the protocol, including the scheduled Follow-up Visit).

5. STUDY POPULATION

Prospective approval of protocol deviations to recruitment and enrollment criteria, also known as protocol waivers or exemptions, is not permitted.

5.1. Inclusion Criteria

Male and female participants are eligible to be included in the study only if all of the following criteria apply:

Age

1. Participants must be ≥ 18 to 55 years of age inclusive, at the time of signing the informed consent.

Type of Participant and Disease Characteristics

2. Participants who are healthy as determined by medical evaluation with no clinically significant or relevant abnormalities as determined by medical history, physical examination, vital signs, 12-lead electrocardiogram (ECG), and clinical laboratory evaluation (hematology, biochemistry, coagulation, and urinalysis) that are reasonably likely to interfere with the participant's participation in or ability to complete the study, or to potentially confound interpretation of study results, as assessed by the Investigator.
3. Adequate venous access in the left or right arm to allow collection of study-required blood samples.

Weight

4. Body weight ≥ 50 to ≤ 100 kg and BMI within the range 18 to < 32 kg/m² for all participants.

Sex

5. Contraceptive use by men or women should be consistent with local regulations regarding the methods of contraception for those participating in clinical studies.
 - a. Male participants:
 - Male participants, if heterosexually active and with a female spouse or partner of childbearing potential or a pregnant or breastfeeding spouse or partner, must agree to use barrier contraception (male condom) for the duration of the study and for at least 3 months after the end of systemic exposure of the study intervention (ie, 3 months after the EOS Visit). Male participants must not donate sperm for at least 3 months after the end of systemic exposure of the study intervention (ie, 3 months after the EOS Visit).
 - Female spouses or partners of male participants who are of childbearing potential must use highly effective contraception as defined in Section 10.4 starting at least 6 weeks before (the male participant's) first study intervention administration and continuing until at least 3 months after the end of their male partner's systemic exposure to the study intervention (ie, 3 months after the EOS Visit).

- Barrier contraception is required even with documented medical assessment of surgical success of a vasectomy. For male participants who have had a vasectomy (with documented evidence of azoospermia if possible) and agree to use a barrier method (male condom) for the stated time period, no additional contraceptive method is required by their female partner.
- b. Female participants:
 - Female participants or female partners of male participants of childbearing potential (including breastfeeding females), if heterosexually active, must be willing to follow protocol specified contraception guidance starting at least 6 weeks before first study intervention administration and continuing for at least 3 months after the end of systemic exposure of the study intervention (ie, 3 months after the EOS Visit). Female participants must not donate ova for at least 3 months after the EOS (ie. 3 months after the EOS Visit).
 - Female participants who are documented as being of non-childbearing potential as defined in Section 10.4 are exempt from contraception requirements.
 - Highly effective contraceptive methods for female participants and female partners of male participants are detailed in Section 10.4.

Informed Consent

6. Capable of giving signed informed consent as described in Section 10.1.3 which includes compliance with the requirements and restrictions listed in the informed consent form (ICF) and in this protocol.

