8.2.6. Pregnancy

- Pregnancy data from female participants and female spouses/partners of male participants will be collected from the first dose of study intervention through 3 months postdose. Any female participant who becomes pregnant while participating in the study will be discontinued from the study intervention. If a pregnancy is reported, the Investigator must immediately inform Alexion within 24 hours of awareness of the pregnancy and follow the procedures outlined in Section 10.4.
- For all Alexion products, both in development or post approval, exposure during pregnancy must be recorded and the pregnancy followed until the outcome of the pregnancy is known (ie, spontaneous miscarriage, elective termination, normal birth, or congenital abnormality), even if the participant discontinues the study intervention or withdraws from the study. The corresponding infant must be followed for 3 months postpartum.
- Pregnancy is not considered as an AE (Section 10.3.1) unless there is a suspicion that the study intervention may have interfered with the effectiveness of a contraceptive medication. However, complications of pregnancy and abnormal outcomes of pregnancy are AEs and may meet the criteria for an SAE (eg, ectopic pregnancy, spontaneous abortion, intrauterine fetal demise, neonatal death, or congenital anomaly) (Section 10.3). Elective abortions without complications should not be reported as AEs.

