10.4. Appendix 4: Contraceptive Guidance and Collection of Pregnancy Information

CONTRACEPTIVES^a ALLOWED DURING THE STUDY INCLUDE:

 ● Highly Effective Methods^b That Have Low User Dependency

 ● Implantable progestogen-only hormone contraception associated with inhibition of ovulation^c

 ● Intrauterine device (IUD): female participants with a Cu-containing IUD are excluded from study

 ● Intrauterine hormone-releasing system (IUS)^c

 ● Bilateral tubal occlusion

 ● Vasectomized partner 
 ○ (Vasectomized partner is a highly effective contraceptive method provided that the partner is the sole sexual partner of the woman of childbearing potential and the absence of sperm has been confirmed. If not, an additional highly effective method of contraception should be used. Spermatogenesis cycle is approximately 90 days.)

 ● Highly Effective Methods^b That Are User Dependent

 ● Combined (estrogen- and progestogen-containing) hormonal contraception associated with inhibition of ovulation^c 
 ○ Oral ○ Injectable ○ Intravaginal ○ Transdermal

 ● Progestogen-only hormone contraception associated with inhibition of ovulation^c 
 ○ Oral ○ Injectable

 ● Sexual abstinence 
 ○ (Sexual abstinence is considered a highly effective method only if defined as refraining from heterosexual intercourse during the entire period of risk associated with the study intervention. The reliability of sexual abstinence needs to be evaluated in relation to the duration of the study and the preferred and usual lifestyle of the participant.)

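### Section 5.1 waives the partner's contraceptive method for a vasectomised participant without requiring confirmed absence of sperm, which Section 10.4 makes the condition for relying on vasectomy

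*Protocol*

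**What the plan says.** **Male participants, general rule (Protocol 5.1, criterion 5a).** A heterosexually active man with a partner of childbearing potential uses a condom, and the partner "must use highly effective contraception as defined in Section 10.4". She starts at least 6 weeks before his first dose and continues until 3 months after the EOS Visit. Criterion 5b adds: "Highly effective contraceptive methods for female participants and female partners of male participants are detailed in Section 10.4".

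**Male participants, vasectomy exception (Protocol 5.1, criterion 5a).** The condom stays mandatory even when surgical success has been documented. The partner's duty is lifted: "For male participants who have had a vasectomy (with documented evidence of azoospermia if possible) and agree to use a barrier method" for the stated period, "no additional contraceptive method is required by their female partner".

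**The standard (Protocol 10.4).** A vasectomised partner is listed among the highly effective methods on two conditions: he is the woman's sole sexual partner, and "the absence of sperm has been confirmed. If not, an additional highly effective method of contraception should be used". The male condom is not on the list.

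**Pregnancy data (Protocol 8.2.6).** Pregnancies in participants and partners "will be collected from the first dose of study intervention through 3 months postdose". The section also says: "If a pregnancy is reported, the Investigator must immediately inform Alexion within 24 hours of awareness of the pregnancy". Exposed pregnancies are followed to their outcome.

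**The concern.** Section 5.1 makes 10.4 the reference for partners of male participants and then grants a waiver on looser terms than 10.4 allows. Evidence of azoospermia is asked for only where it can be had, and nothing else in 5.1 makes confirmation a condition. A man whose vasectomy was never checked for success can therefore meet the criterion while his partner uses nothing.

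What is at stake is partner safety in a subset of couples, and consistent application of an eligibility criterion. Section 5 does not permit waivers of the criteria, so a site must apply the sentence as it stands.

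A smaller, separate matter is that 5.1 and 8.2.6 count their three months from different points, so the contraception period and the pregnancy-collection period do not end together.

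**Working it through.** **Vasectomy: the three kinds of couple side by side** (man with a partner of childbearing potential)

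| Couple | Condom (5.1) | Partner method required by 5.1 | Is a 10.4 highly effective method in place? |
|---|---|---|---|
| No vasectomy | Yes | Yes, from the 10.4 list | Yes |
| Vasectomy, absence of sperm confirmed, sole partner | Yes | None | Yes, the vasectomy itself |
| Vasectomy, absence of sperm not confirmed | Yes | None | No; 10.4 calls for an additional method |

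The condom is common to all three rows, so it cannot stand in for what is missing in the third. Section 5.1 also leaves out 10.4's sole-partner condition.

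**Lead time if the waiver is narrowed.** Section 5.1 asks for the partner's method from at least 6 weeks = 42 days before the first dose. Screening lasts up to 28 days (Synopsis). A couple who begin a method at Screening are therefore at least 42 − 28 = 14 days short.

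**The two windows.** Inputs: the EOS Visit is 14 ± 2 days after the last dose (Synopsis; 4.4 gives Day 15 ± 2), contraception ends 3 months after EOS (5.1), and collection ends 3 months postdose (8.2.6). Assumptions: postdose means after the last dose, and 3 months = 91 days.

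- End of contraception: 91 + 12, 14 or 16 = 103, 105 or 107 days after the last dose.
- End of collection: 91 days.
- Gap: 12, 14 or 16 days, which is 12/103 = 11.7%, 14/105 = 13.3% or 16/107 = 15.0% of the period after the last dose.

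Using 90 or 92 days for 3 months leaves the gap in days unchanged. With true calendar months it is usually the same, and 10 to 19 days at the extremes. The protocol does not define postdose. Counted from the first dose, with two washouts of at least 14 days, the gap is at least 28 + 12 to 28 + 16 = 40 to 44 days.

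**Exposure left in that gap.** Section 4.2 puts average removal of plasma total Mo at about 99.2% or more in 14 days.

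- Half-lives in 14 days: ln(1/0.008)/ln 2 = 6.97.
- One half-life: 14/6.97 ≈ 2.01 days.
- Half-lives elapsed by day 91: 91/2.01 ≈ 45.

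On that figure the drug exposure in the uncollected days is negligible.

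**The case against.** **The condom rule may be deliberate.** Section 10.4 rates vasectomy as a stand-alone method, while 5.1 pairs it with a compulsory condom, which could be read as a two-method rule designed for male participants. That reduces the practical risk, and this part of the objection stands. It does not remove the discrepancy: 5.1 itself sends partners of male participants to 10.4, and 10.4 asks for an additional highly effective method, which a condom is not.

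**The phrase may concern paperwork only.** Grammatically, the qualifier attaches to obtaining documented evidence. A man with confirmed absence of sperm whose record cannot be retrieved is the natural case for it, and he is not the concern here. But no other words in 5.1 require confirmation, so the unconfirmed man is eligible too. The closing reference to 10.4 and the opening deference to local regulations might lead a careful site to apply 10.4 anyway. An eligibility criterion should not depend on that.

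**Stronger readings of 8.2.6.** A reader might infer that 8.2.6 falls short of a standard the protocol sets itself, or that pregnancies would be lost. The documents support neither. No sentence requires collection to match the contraception period. Pregnancies that become known must be reported within 24 hours of awareness (8.2.6; also 10.3.1 for those during exposure), and exposed pregnancies are followed to outcome. Sections 4.4 and 6.5.2 also mention a Follow-up Visit without giving its timing, so nothing can be said about contact after EOS.

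**Early leavers.** A reader might also infer that participants who leave early have no workable end date. The notes to the Schedule of Activities have EOS procedures performed at early termination and define EOS/ET as one item, so the final visit can serve for both. No section defines the end of systemic exposure as 14 days after the last dose, so a separate rule built on that would have no basis in the protocol.

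**Conclusion.** The vasectomy point holds as a minor participant- and partner-safety wording issue. For vasectomised men without confirmed absence of sperm, 5.1 permits less than 10.4 asks. It affects only such men who have a partner of childbearing potential. The documents do not say how many there will be, so no number is estimated. The conclusion rests on reading 5.1 literally and on taking 10.4 as the standard for partners of male participants, as 5.1 states.

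The mismatch between 5.1 and 8.2.6 is an optional alignment. Its size for a completer, about 12 to 16 days, depends on counting from the last dose. No rule is broken, and the exposure concerned is negligible. Neither matter touches the PK analyses or the sample size.

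**What to change.** **In 5.1:** limit the waiver to vasectomised men whose absence of sperm has been confirmed, by record or by documented medical history. Otherwise require the partner to use another highly effective method from 10.4 for the stated period. Citing 10.4 in the same sentence would carry over its sole-partner condition.

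**Cost:** protocol and consent-form wording. Accepting documented medical history means no semen test has to be added. There is one real downside: a man without confirmation whose partner uses no 10.4 method at Screening would miss the 6-week lead time and be rescreened (5.4) or not enrolled.

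**Optional, in 8.2.6:** replace the three-months-postdose limit with 3 months after the EOS/ET Visit. This settles what postdose means and, for a completer, adds about two weeks of pregnancy collection.

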5.2. Exclusion Criteria

Participants are excluded from the study if any of the following criteria apply:

1. History or presence of/significant history of or current cardiovascular, respiratory, hepatic, renal, gastrointestinal, endocrinological, hematological, or neurological disorders, or psychiatric disorder. Any surgical or medical history which may significantly alter the absorption, metabolism, or elimination of drugs or constitute a risk when taking the study intervention; or interfering with the interpretation of data (eg, gastric bypass, cyclical vomiting, etc).
2. Supine blood pressure $\leq 90/60$ mmHg or $> 140/90$ mmHg at Screening; systolic or diastolic components outside of range should result in exclusion. Supine blood pressure should be taken after a minimum of 5 minutes in supine position. If vital signs are abnormal, 2 additional readings will be taken. The mean of the 3 replicates will be recorded in the case report form (CRF) and used to determine inclusion.
3. Lymphoma, leukemia, or any malignancy within 5 years except for basal cell or squamous epithelial carcinomas of the skin that have been resected with no evidence of metastatic disease for 3 years.
4. Alanine aminotransferase (ALT), aspartate aminotransferase (AST) or total bilirubin $>$ upper limit of normal (ULN) of laboratory reference range at Screening. At the

discretion of the Investigator, a single repeat analysis may be performed to assess eligibility during the Screening period.

5. Serum Cu or serum ceruloplasmin below lower limit of normal on laboratory reference range at Screening.
6. History of anemia or hemoglobin < 130 g/L for men and hemoglobin < 115 g/L for women at Screening. At the discretion of the Investigator, a single repeat analysis may be performed to assess eligibility, with the agreement of the Medical Monitor.
7. History of benign ethnic neutropenia or absolute neutrophil count < 1500/ μ L; lymphocyte < 1000/ μ L.
8. Blood donation or blood loss in excess of 500 mL in the 60 days prior to Screening.
9. QT interval corrected using Fridericia's formula (QTcF) > 450 ms for male participants; QTcF > 470 ms for female participants.
10. Current or chronic history of liver disease or known hepatic or biliary abnormalities (except for asymptomatic gallstones). Participants with elevated total bilirubin or history of Gilbert's will be excluded from the study.
11. Any other significant disease or disorder which, in the opinion of the Investigator, may put the participant at risk or confound the interpretation of the results.
12. History of hypersensitivity to ALXN1840 or its excipients or any significant allergic reaction (eg, anaphylaxis or angioedema) to any product (eg, food, pharmaceutical).

Prior/Concomitant Therapy

13. Use or intended use of prescription medications (excluding oral contraceptives) within 21 days or 5 half-lives of the drug (whichever is longer) prior to Day -1, and/or intended use at any point over the duration of the study except with prior approval of Alexion.
14. Use of nonprescription/ over-the-counter medications, including herbal remedies and supplements, within 7 days or 5 half-lives of the drug (whichever is longer) prior to Day -1 and/or intended use at any point over the duration of the study.

Prior/Concurrent Clinical Study Experience

15. Current enrollment or past participation, within the last 90 days, before signing of consent in this or any other clinical study involving an investigational study intervention or any other type of medical research. Participants, involved in intervention studies using investigation or non-investigational drug with prolonged half-lives, are not eligible unless the time since last treatment has exceeded 90 days or 5 half-lives of the study intervention, whichever is longer.

Diagnostic Assessments

16. Presence of hepatitis B surface antigen or positive hepatitis C antibody or RNA test result at Screening. NOTE: participants with positive hepatitis C antibody due to prior resolved disease can be enrolled if a confirmatory negative hepatitis C RNA test result is obtained. NOTE: The RNA test is optional and participants with negative hepatitis C antibody test are not required to also undergo hepatitis C RNA testing.

17. Positive human immunodeficiency virus (HIV) antibody test.

Other Exclusions

18. Female participants who are pregnant, as evidenced by a positive serum pregnancy test result at Screening, or breastfeeding.
19. Prior exposure to ALXN1840.
20. Major surgery or hospitalization within 90 days prior to dosing on Day 1.
21. Use of tobacco in any form (eg, smoking, chewing or vaping), other nicotine-containing products in any form (eg, gum, patch, electronic cigarettes, or vapes), or any recreational inhalational product within 6 months prior to the planned first day of dosing.
22. Use of known drugs of abuse within 6 months prior to the planned first day of dosing.
23. Regular alcohol consumption within 6 months prior to the study defined as: an average weekly intake of > 14 units/week for males or > 7 units/week for females. One unit is equivalent to 8 g of alcohol: a half pint (~240 mL) of beer, one ~4 oz glass (125 mL) of wine or 1 (25 mL) measure of spirits.
24. Positive urine drug toxicology screen at Screening or check-in (Day -1).
25. Alcohol consumption within 24 hours prior to study intervention administration or positive alcohol breath test at Screening or check-in (Day -1).
26. Sensitivity to any of the study interventions, or components thereof, or drug or other allergy that, in the opinion of the Investigator or Medical Monitor, contraindicates participation in the study.

